### **3.7.4      End of Trial**

The end of trial date is defined as the last date of contact or the date of final contact attempt from the post-treatment follow-up eSource page for the last subject completing or withdrawing from the trial.

### **3.7.5      Independent Data Monitoring Committee**

A data monitoring committee (DMC) will provide oversight for safety monitoring. The details of the DMC structure and its roles and responsibilities will be documented in a DMC charter.

## **3.8      Stopping Rules, Withdrawal Criteria, and Procedures**

### **3.8.1      Entire Trial**

If the sponsor terminates or suspends the trial for any reason, prompt notification will be given to investigators, IRBs/IECs, and regulatory authorities in accordance with regulatory requirements.

### **3.8.2      Individual Site**

Individual trial site participation may be discontinued by the sponsor, the investigator, or the IRB/IEC if judged to be necessary for medical, safety, regulatory, ethical or other reasons consistent with applicable laws, regulations, and GCP. A particular trial site may be terminated from the trial at the discretion of the investigator, sponsor, or IRB/IEC, eg, for non-enrollment of subjects or noncompliance with GCP or with the protocol. The investigator will notify the sponsor promptly if the trial is terminated by the investigator or the IRB/IEC at the site.

### **3.8.3 Individual Subject Discontinuation**

#### **3.8.3.1 Treatment Interruption**

All attempts should be made to avoid treatment interruption during the trial. For subjects who have an interruption of treatment, the investigator or designee will contact the sponsor at the earliest possible time by telephone. The sponsor should be notified when there is a planned or inadvertent treatment interruption of 4 days or more in a 7-day period. The investigator and sponsor will come as quickly as possible to a joint decision regarding the subject's continuation in the trial. This decision will be documented by the investigator and the sponsor, and reviewed by the site monitor. The treatment interruption will be recorded in the eSource and also recorded as a protocol deviation ([Section 3.13](#)).

#### **3.8.3.2 Treatment Discontinuation**

After starting open-label IMP, a subject may stop treatment permanently for a variety of reasons. Treatment discontinuations may be initiated by a subject who is not satisfied with treatment or may become medically necessary due to AEs, required treatment with a disallowed medication or therapy, or other issues, as determined by the investigator. However, each investigator must comprehensively review the circumstances and offer the subject options for continued treatment to the degree possible as described in [Section 3.8.3.5](#).

If a subject discontinues from the trial prematurely, the reason must be fully evaluated and recorded appropriately in source documents and in eSource. If the subject is being withdrawn because of an AE, that AE should be indicated as the reason for withdrawal. All subjects have the right to withdraw at any point during treatment without prejudice. The investigator can discontinue a subject's participation in the trial at any time if medically necessary.

#### **3.8.3.3 Documenting Reasons for Treatment Discontinuation**

A subject may discontinue IMP for a number of reasons including those listed below:

- Reasons related to AE:
  - Subject decides to discontinue because of annoyance or discomfort due to a non-serious AE which is not otherwise determined to be an undue hazard
  - Continuing IMP places the subject at undue risk as determined by the investigator (eg, a safety concern that is possibly, probably, or likely related to IMP)

- Serious TEAE
- Clinical worsening, suicidality, and unusual changes in behavior, and the risk of increased suicidality
- Death
- Reasons unrelated to medical condition (provide detail and review AE history with subject)
- Withdrawal of informed consent
- Lost to follow-up
- Pregnancy (see [Section 5.5](#))
- Termination of all or part of the trial by the sponsor

If the subject discontinues IMP due to an AE, the investigator, or other trial personnel, will make every effort to follow the event until it has resolved or stabilized.

#### **3.8.3.4      Withdrawal of Consent**

All subjects have the right to withdraw their consent from further participation in the trial at any time without prejudice. Subjects' parents or legal guardians can also withdraw their consent to allow subjects to continue participation in the trial. Subjects or parents/legal guardians cannot withdraw consent for use of data already collected as part of the trial, but only for future participation. The investigator can also discontinue a subject's participation in the trial at any time if medically necessary. Unless the subject provides their written withdrawal of consent or there is other written documentation by the investigator confirming the subject's verbal intent to completely withdraw from the trial, subjects should be followed for all protocol-specified evaluations and assessments, if possible.

Complete withdrawal of consent requires a subject's refusal of ALL of the following methods of follow-up:

- Participation in all follow-up procedures specified in the protocol (whether in-clinic, by telephone, or by an in-home visit).
- Participation in a subset of protocol specified follow-up procedures (by a frequency schedule and method, as agreed by subject and staff).
- Contact of the subject by trial personnel, even if only by telephone, to assess current medical condition, and obtain necessary medical or laboratory reports relevant to the trial's objectives.

- Contact of alternative person(s) who have been designated in source records as being available to discuss the subject's medical condition, even if only by telephone, mail, or e-mail (eg, family, spouse, partner, legal representative, friend, neighbor, or physician).
- Access to medical information from alternative sources (eg, hospital/clinic medical records, referring doctor's notes, public records, dialysis, transplantation or vital registries, social media sources).

Withdrawal of consent is a critical trial event and therefore should be approached with the same degree of importance and care as is used in initially obtaining informed consent. The reasons for a subject's intended withdrawal need to be completely understood, documented, and managed to protect the rights of the subject and the integrity of the trial. A subject may initially express their desire to interrupt or discontinue IMP administration (see [Section 3.8.3.1](#)), which is not equivalent to a complete withdrawal of consent for further participation (see [Section 3.8.3.2](#)). A subject may, however, indicate that further trial participation is creating a burden on their work or social schedule. Therefore, the investigator should follow the procedures outlined in [Section 3.8.3.3](#) to determine if the subject can continue participation in the trial if modifications to his/her treatment or schedule of assessments can be accommodated. Only subjects who withdraw their permission for all of the above degrees of follow-up are considered to have completely withdrawn their consent to participate in the trial.

### **3.8.3.5 Procedures to Encourage Continued Trial Participation**

In all cases of impending IMP discontinuation or consent withdrawal, investigators will be given instructions to meet and discuss with the subject their options of continuing in the trial, preferably on therapy. The investigator should ensure understanding and documentation of the reasons for the subject's desire to withdraw consent.

### **3.9 Screen Failures**

A screen failure subject is one from whom informed consent is obtained and is documented in writing (ie, subject signs an ICF), but who is not started on brexpiprazole treatment. For the purposes of this trial, treatment begins with the first dose of oral brexpiprazole during the conversion period or open-label treatment period.

Subjects who fail to qualify for the trial during screening for a reason other than a positive screen for drugs of abuse may be eligible to be rescreened one additional time at a later date. The medical monitor must be contacted before the rescreening of any de novo subject. In the event that a de novo subject is rescreened for trial participation, a

new ICF must be signed and a new screening number assigned. If a de novo subject previously participated in Trial 331-10-234, they will retain their subject identification number from Trial 331-10-234.

### **3.10      Definition of Completed Subjects**

The treatment period is defined as the time period during which subjects are evaluated for primary and secondary objectives of the trial irrespective of whether or not the subject actually consumed all doses of the IMP. Subjects who are evaluated at the last scheduled visit during the treatment period will be defined as trial completers. For purposes of this trial, subjects who complete Month 24 will be defined as trial completers.

### **3.11      Definition of Subjects Lost to Follow-up**

Subjects who cannot be contacted on or before Month 24 during the treatment period, who do not have a known reason for discontinuation (eg, withdrew consent or AE), and for whom a survival status at the end of the trial cannot be determined will be classified as “lost to follow-up” as the reason for discontinuation. Survival status can be determined from a variety of sources, either by obtaining acceptable documentation for death (ie, death certificate, medical records, public records, statement by a family member or primary care physician) or acceptable documentation for life (ie, direct contact with the subject, medical records, successful telephone contact with the subject, statement by a family member or primary care physician, or public records).

The site will make 3 documented attempts to contact the subject by telephone and in the event the site is unable to reach the subject by telephone, the site will attempt to contact the subject via certified mail or an alternative similar method, where appropriate, before assigning a “lost to follow-up” status.

### **3.12      Subject Compliance**

Responsible trial personnel will dispense the IMP (open-label brexpiprazole) to subjects. Accountability and compliance verification should be documented in the subject’s trial records. Subjects must be counseled on the importance of taking the IMP as directed at all trial visits. If poor compliance continues (eg, multiple missed doses resulting in less than 80% overall compliance), discontinuation of the subject from the trial should be considered.

### **3.13 Protocol Deviations**

This trial is intended to be conducted as described in this protocol. In the event of a significant deviation from the protocol due to an emergency, accident, or mistake (eg, violation of informed consent process, IMP dispensing or subject dosing error, treatment assignment error, subject enrolled in violation of eligibility criteria or concomitant medication criteria), the investigator or designee will contact the sponsor (or designee) at the earliest possible time by telephone. The investigator and sponsor will come as quickly as possible to a joint decision regarding the subject's continuation in the trial. This decision will be documented by the investigator and the sponsor, and reviewed by the site monitor.

## **4 Restrictions**

### **4.1 Prohibited Medications**

All subjects must agree to abstain from prohibited medications during the trial. Prohibited medications for de novo subjects are listed in [Table 4.1-1](#). Other therapies prohibited prior to enrollment and during the trial are presented in [Section 4.2](#).

| Table 4.1-1 Washout of Prohibited Medications Required Before the Trial - De Novo Subjects  |   |
|--|---|
| Medication  | Required Washout Prior to Open-label Treatment Period  |
| Antipsychotics
Oral aripiprazole
Oral antipsychotics (other than cariprazine and clozapine)
Depot or long-acting injectable antipsychotics
Cariprazine (Vraylar) and clozapine | 14 days
7 days
5 × half-lives of the medication
6 months                                     |
| Antidepressants
Fluoxetine or Symbax
MAOIs
Citalopram and escitalopram
Venlafaxine and desvenlafaxine
All other antidepressants   | 28 days a
14 days
8 days
3 days
14 days  |
| Atomoxetine
Stimulants  | 28 days with the diagnosis of ADHD;
minimum 5× half-life for subjects
without diagnosis of ADHD |
| Mood stabilizers (ie, lithium or anticonvulsants)  | 7 days  |
| Varenicline  | 5 days  |
| Oral benzodiazepines used as rescue therapy during washout b
Lorazepam, oxazepam, diazepam, or clonazepam
Other benzodiazepines   | 12 hours before scales c
14 days  |
| CYP2D6 inhibitors and CYP3A4 inhibitors and inducers
(see Table 4.1-4 )   | 14 days   |

MAOIs = monoamine oxidase inhibitors.

aExtension to the screening window is needed for washout, contact the medical director.

bUse of IM benzodiazepines and continual use of oral benzodiazepines are prohibited throughout the trial. However, limited use of specific oral benzodiazepines is permitted during screening to treat agitation or insomnia (see [Table 4.1-3](#)).

cBenzodiazepines must not be administered within 12 hours prior to scheduled efficacy and safety assessments, including EPS scales. Investigators are encouraged to delay scale administration until 12 hours have elapsed, if at all possible. However, if delaying administration of efficacy and safety scales is not feasible, the scales should still be administered and the use of benzodiazepine documented, including a notation of the drug name, dose, and time of administration on the eSource.

[Table 4.1-2](#) lists all medications prohibited during the trial, including exceptions, where appropriate.

| Table 4.1-2 List of Medications Prohibited During the Trial |   |
|--|---|
| 1.   | All psychotropic agents including, but not limited to, the following:
a) Antipsychotics, including IR IM and depot or long-acting injectable formulations
b) Antidepressants (including MAOIs)
c) Symbax or fluoxetine
d) Mood stabilizers (ie, lithium or anticonvulsants)
e) Benzodiazepines, except specific benzodiazepines when used as rescue therapy a
f) Stimulants b
g) Other psychotropics (ie, atomoxetine) |
| 2.   | Ramelteon and other non-benzodiazepine sleep aids, except for limited use of specific medications for the treatment of insomnia c  |
| 3.   | Antihistamines (except for loratadine and cetirizine)   |
| 4.   | Varenicline   |
| 5.   | Other nutritional supplements and nonprescription herbal preparations with central nervous system effects (eg, St. John's Wort, omega-3 fatty acids, kava extracts, GABA supplements) unless approved in advance by the medical monitor.  |
| 6.   | CYP2D6 inhibitors and CYP3A4 inhibitors and inducers (see Table 4.1-4 )   |
| 7.   | Investigational agents  |

GABA = gamma-aminobutyric acid; IR = immediate-release.

aUse of IM benzodiazepines and continual use of oral benzodiazepines are prohibited throughout the trial. However, limited use of specific oral benzodiazepines is allowed for the control of agitation or insomnia as shown in [Table 4.1-3](#).

bOnly for de novo subjects: Stimulants with the diagnosis of ADHD and treatment with stimulants within 28 days prior to screening; otherwise washout of  $> 5 \times$  half-life for subjects without diagnosis of ADHD.

cNon-benzodiazepine sleep aids (ie, zolpidem, zaleplon, zopiclone, and eszopiclone only) are permitted for the treatment of insomnia, but not on the same day as administration of a benzodiazepine, regardless of indication. For the non-benzodiazepine sleep aids, sites should only utilize one of the listed medications that are approved for this indication in their respective countries and the country-specific prescribing information is to be used to determine the maximum allowable daily dose for the treatment of insomnia. Non-benzodiazepine sleep aids must not be administered within 12 hours prior to scheduled efficacy and safety assessments, including EPS scales. Investigators are encouraged to delay scale administration until 12 hours have elapsed, if at all possible. However, if delaying administration of efficacy and safety scales is not feasible, the scales should still be administered and the use of the sleep aid documented, including a notation of the drug name, dose, and time of administration on the eSource.

During the course of the trial, oral benzodiazepine rescue medication can be used for symptomatic relief based on the investigator's judgment with the exceptions and restrictions outlined in [Table 4.1-3](#). All concomitant medications should be prescribed according to the respective drug labels. Subjects who are started on therapy should be observed closely for clinical worsening, suicidality, and unusual changes in behavior, and the risk of increased suicidality must be balanced with the clinical need.

| Oral Benzodiazepine | Maximum Allowable Dose (mg/day) |
|----------------------------|--|
|                            | Screening to Month 24 Visit     |
| Lorazepam a     | 3                                      |
| Oxazepam a      | 45                                     |
| Diazepam a,b    | 15                                     |
| Clonazepam a,b  | 1.5                                    |

aBenzodiazepines must not be administered within 12 hours prior to scheduled efficacy and safety assessments, including EPS scales. Investigators are encouraged to delay scale administration until 12 hours have elapsed, if at all possible. However, if delaying administration of efficacy and safety scales is not feasible, the scales should still be administered and the use of benzodiazepine documented, including a notation of the drug name, dose, and time of administration on the eSource.

bIn countries or institutions where no short-acting benzodiazepines are commercially available, use of oral diazepam or oral clonazepam may be acceptable if prior authorization is obtained from the medical monitor.

**Table 4.1-4** below provides a select list of CYP2D6 inhibitors and CYP3A4 inhibitors and inducers which are prohibited within 14 days of first dose of IMP and for the duration of the trial. Except for episodic use of ibuprofen, acetaminophen/paracetamol, naproxen, or equivalent, clinical sites must apprise the medical monitor of the use of all over-the-counter medications including supplements and vitamins. Any medication needing to be used in a chronic manner requires discussion with the medical monitor.

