### **1.2.1 Pharmacokinetics/Pharmacodynamics**

The PK of single and multiple doses of brexpiprazole was studied in healthy subjects and in subjects with MDD, attention-deficit/hyperactivity disorder (ADHD), and schizophrenia or schizoaffective disorder. Based on preclinical data and human clinical trials, brexpiprazole (OPC-34712) and one metabolite, DM-3411, were identified as the major analytes that are present in human plasma. In vitro, the activity of DM-3411 is 17 times lower than that of brexpiprazole and thus is considered as an inactive metabolite. Both brexpiprazole and DM-3411 PK were linear following single oral doses of brexpiprazole 0.2 to 8 mg to healthy subjects. The terminal phase elimination half-life of brexpiprazole and DM-3411 was 48.3 to 80.8 hours and 48.6 to 77.5 hours, respectively. The median time to maximum (peak) plasma concentration ( $t_{max}$ ) occurred at approximately 2 to 6 hours postdose for brexpiprazole and at approximately 10 to 24 hours postdose for DM-3411. In healthy subjects, administration of single-dose brexpiprazole with a high-fat meal did not affect its rate and extent of absorption.

Steady state PK also appeared to be linear following multiple daily doses of brexpiprazole in the range of 0.5 to 2 mg to healthy subjects. The accumulation factor based on maximum (peak) plasma concentration and area under the concentration-time curve calculated to the last observable concentration at time  $t$  was approximately 4 times. After multiple dose administration of brexpiprazole (1 to 12 mg/day) to subjects with schizophrenia or schizoaffective disorder, brexpiprazole and DM-3411 mean terminal elimination half-life at steady state was 95.4 and 89.3 hours, respectively; median  $t_{max}$  was 3.0 and 8.0 hours, respectively.

In drug interaction trials in healthy subjects, brexpiprazole was shown to be metabolized by cytochrome P450 (CYP) 3A4 and CYP2D6 isozymes and was not an inhibitor of CYP3A4, CYP2B6, CYP2D6, or P-glycoprotein. Co-administration of potent CYP3A4 or CYP2D6 inhibitors with brexpiprazole resulted in about a 2-fold higher exposure and about a 1.5-fold increase in the terminal elimination half-life of brexpiprazole.

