### **3.2.2.2      Open-label Treatment Period**

Timing of the first dose of brexpiprazole in the open-label treatment period for de novo subjects will be as follows:

- De novo subjects who participate in the 1- to 4- week conversion period, will receive open-label brexpiprazole in the open-label treatment period once all prohibited medications are discontinued during the conversion period per [Table 4.1-1](#) and once all baseline evaluations are completed.
- De novo subjects who are able to complete the required washout of prohibited medications per [Table 4.1-1](#) will receive the first dose of open-label brexpiprazole in the open-label treatment period as soon as all screening and baseline evaluations are completed.

De novo subjects who participated in the conversion period will begin dosing with brexpiprazole 1, 2, or 3 mg/day in the open-label treatment period. If this dose is well tolerated, but the response is inadequate, weekly dose increases can be made in 1 mg

increments up to a maximum dose of 4 mg/day, based on the clinical judgment of the investigator.

Daily dosing for this trial includes 1, 2, 3, or 4 mg.

The maximum dose of brexpiprazole to be used in this trial is 4 mg daily. The dose of brexpiprazole may be decreased at any time based on the investigator's judgment after the start of the open-label treatment period. Dose decreases will occur in 1 mg decrements, with the frequency of the 1 mg decreases based upon tolerability. Those unable to tolerate the minimum 1 mg daily dose of brexpiprazole must be withdrawn from the trial. The dosing strategy is summarized in [Table 3.2.2.2-1](#). Rechallenge with higher doses of brexpiprazole (in 1 mg/day increments) is permitted following dose decreases, if clinically warranted based on the investigator's judgment.

Dose adjustments must ultimately be made based upon the clinical judgment of the investigator as it relates to tolerability and therapeutic response.

| Table 3.2.2.2-1 Dose Adjustments for Brexpiprazole in the Open-label Treatment Period for De Novo Subjects after Conversion |                      |  |
|--|----------------------|--|
| Trial Visit   | Dose Options  | Dose Changes  |
| Start of the open-label treatment period, Days 1–7   | 1, 2, or 3 mg/day    | Maintain same dose, or option to increase or decrease dose by 1 mg/day (minimum dose 1 mg/day)                           |

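### For de novo subjects who convert, the washout of CYP-interacting drugs has two incompatible anchors (first IMP dose and open-label entry); the 28-day stimulant rule in ADHD has a similar conflict

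*Protocol*

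**What the plan says.** **CYP inhibitors and inducers**

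- Protocol Section 4.1, in the text introducing Table 4.1-4, calls the listed drugs ones "which are prohibited within 14 days of first dose of IMP and for the duration of the trial".
- Section 3.9 fixes when IMP starts: "treatment begins with the first dose of oral brexpiprazole during the conversion period or open-label treatment period". For converters, Table 3.2.2.1-1 and Table 3.7-2 put that at conversion baseline.
- Table 4.1-1 has the column heading "Required Washout Prior to Open-label Treatment Period". Its row for "CYP2D6 inhibitors and CYP3A4 inhibitors and inducers" gives 14 days.
- Sections 3.1, 3.2.2, 3.2.2.1 and 3.7.1.1.2.2 name washout per Table 4.1-1 as a purpose or goal of conversion. Section 3.2.2.2 starts open-label dosing for converters "once all prohibited medications are discontinued during the conversion period per" Table 4.1-1.
- De novo inclusion criterion 11 checks washout only before entry into the open-label period.
- Section 1.2.1 reports that potent CYP3A4 or CYP2D6 inhibitors "resulted in about a 2-fold higher exposure" of brexpiprazole.

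**Stimulants in subjects with ADHD (de novo)**

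- Table 4.1-1 gives 28 days, under the same open-label heading.
- Table 4.1-2, footnote b, counts from screening: "Stimulants with the diagnosis of ADHD and treatment with stimulants within 28 days prior to screening".
- Inclusion criterion 4 bars treatment within 28 days and names no reference date.

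**The concern.** A site can follow one current passage faithfully and breach another. A converter who stops a listed inhibitor during the first days of conversion meets Table 4.1-1 if 14 days then pass before open-label Day 1, yet breaks the Section 4.1 text. No passage says which prevails.

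What is at stake is who may take brexpiprazole while an interacting drug is present or only recently stopped. AEs in the conversion period get their own summary (SAP Sections 8 and 8.1.2). According to footnote b of SAP Figure 3-2, the last conversion dose becomes the open-label starting dose. A dose settled on while an inhibitor or inducer was still acting may correspond to a different exposure once that drug has gone.

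For ADHD, the screening anchor rules out washout within the trial, while Table 4.1-1 provides for it. The same adolescent can be eligible at one site and ineligible at another.

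**Working it through.** The plan gives no figure to reproduce. The check is to set the anchors side by side and count days.

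**CYP drugs.** Measure time in days from the first conversion dose (day 0), so that open-label Day 1 falls at day L, where L is the conversion length. Section 3.2.2.1 gives 1 to 4 weeks, so L = 7 to 28.

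- Section 4.1 text: last permitted day of the interacting drug = 0 − 14 = −14.
- Table 4.1-1: last permitted day = L − 14.
- Difference between anchors = (L − 14) − (−14) = L.
- Under Table 4.1-1, drug-free days before the first brexpiprazole dose = max(0, 14 − L), and days of overlap = max(0, L − 14).

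| L (days) | Last day, Section 4.1 text | Last day, Table 4.1-1 | Drug-free days before first dose, Table 4.1-1 | Overlap, Table 4.1-1 |
|---|---|---|---|---|
| 7 | −14 | −7 | 7 | 0 |
| 14 | −14 | 0 | 0 | 0 |
| 21 | −14 | 7 | 0 | 7 |
| 28 | −14 | 14 | 0 | 14 |

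These counts hold to within a day or so, and visit windows of ± 3 days apply. A subject who meets Table 4.1-1 at its limit breaches the Section 4.1 text at every conversion length, including 7 days, where there is no overlap. For de novo subjects who skip conversion the two anchors coincide.

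**Dose during the overlap.** Overlap can occur only in about the first 14 days. Reading each column of Table 3.2.2.1-1 as the dose from that visit onward, those days carry 0.5 mg/day and then 0.5 or 1 mg/day. With the protocol's factor of about 2 for potent inhibitors, exposure is roughly that of 2 × 0.5 = 1 to 2 × 1 = 2 mg/day. The table is a recommendation: Section 3.2.2.1 also allows up to 3 mg/day in cross-titration without tying that dose to a week. I found no exposure figure for inducers in the protocol.

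**Stimulants with ADHD.** Let S be the screening length (3 to 28 days, extendable under Section 3.7.1.1.2.1) and K the conversion length (none, or 7 to 28 days). The screening and open-label anchors differ by S + K, so by at least 3 days. Example: a last dose 10 days before screening is barred by footnote b because 10 < 28, but meets Table 4.1-1 if 18 more days pass before open-label Day 1 (10 + 18 = 28).

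**The case against.** The best defence is that the rules are cumulative: a site that meets the Section 4.1 text automatically meets Table 4.1-1. That is true arithmetically, but no passage says the strictest rule governs, and the conversion sections point sites to Table 4.1-1.

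Conversion can also be read as concerning antipsychotics only. Section 3.2.2.1, inclusion criterion 10 and the body of SAP Figure 3-2 lean that way. But footnote a of the same figure, and protocol Sections 3.2.2, 3.2.2.2 and 3.7.1.1.2.2, speak of prohibited medications generally. Table 4.1-2 bars CYP drugs during the trial, but it equally bars antipsychotics, which conversion expressly continues, so it cannot settle what may overlap. De novo exclusion criterion 20 covers subjects likely to need such drugs during the trial, not those able to stop.

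A reader might infer more than the documents support:

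- *Exposure of about 6 mg/day.* Doubling the 3 mg/day allowed in conversion gives 6, above the 4 mg/day trial maximum. Under the recommended scheme 3 mg first appears at Week 3, after Table 4.1-1 would already have ended the overlap. It is a corner case that needs departure from that scheme, not the general size.
- *Distortion of the open-label primary AE data.* The SAP reports conversion AEs separately, and open-label TEAEs start or worsen after open-label entry (Section 8.1.1). By then even Table 4.1-1 requires 14 days free of these drugs.
- *Fluoxetine as an example.* It has its own 28-day row, with a footnote directing an extension of screening. Counted from open-label Day 1, 28 days leaves essentially no overlap within 4 weeks.
- *A contradiction for anticonvulsants that are also listed CYP3A4 inducers, such as carbamazepine.* The 7-day and 14-day rows are both met at 14 days. This is a matter of clarity only.
- *A 56-day ceiling on the stimulant gap (28 + 28).* Screening can be extended, so 56 is not a maximum.

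**Conclusion.** Two inconsistencies stand in the current protocol text. For converting de novo subjects, the CYP washout has two anchors that differ by 7 to 28 days. In a 28-day conversion this is the difference between no co-administration and up to about 14 days of it. For de novo subjects with ADHD, the 28-day stimulant rule has two different anchors and one unstated, at least 3 days apart.

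The consequence is real but limited. It concerns converter safety, conversion-period AEs and possibly the dose carried into open-label treatment. The documents do not state how many subjects are affected. SAP Section 8.1.2 anticipates a small number in conversion, and Section 10.7 drops conversion tables if there are 5 or fewer. The exposure argument assumes a potent inhibitor and the protocol's own 2-fold figure. Nothing here says which anchor or length is right, only that the passages must be reconciled.

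**What to change.** Give each drug class one anchor and state it identically in Table 4.1-1, the Section 4.1 text, Table 4.1-2 footnote b, inclusion criterion 4 and Sections 3.2.2 to 3.2.2.2. The clearest form is to split the washout column of Table 4.1-1 in two: rows to be met before the first IMP dose, including conversion, and rows to be met before open-label Day 1. The sponsor chooses the anchor and the length for each class.

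Optionally, add a sentence saying which row governs a drug that falls in two rows.

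The cost is amendment wording and one table column. Depending on the sponsor's choice, a few de novo subjects may need a slightly longer screening period.
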